
• Summary measures of palbociclib treatment patterns, including:
○ Starting dose.○ Proportion of patients with dose reductions at 1, 2 and 3 years after initiation.○ Proportion of patients with palbociclib treatment discontinuation at 1, 2 and 3 years after initiation.○ Mean (Standard Deviation [SD]) dose intensity over the course of treatment in patients who complete treatment of palbociclib○ Median time to dose reduction in number of days (from start of treatment) and in terms of number of cycles (completed or interrupted).○ Median time to dose increase in number of days (from start of treatment) and in terms of number of cycles (completed or interrupted); only in patients with previously reduced dose○ Median time to palbociclib discontinuation ('drug survival') in number of days (from start of treatment) and in terms of number cycles (completed or interrupted).○ Reasons for discontinuation.○ 1st, 2nd and 3rd line of treatment after progression: number of patients prescribed each medication, dose, and length of treatment.• Description of the number of patients which are being prescribed as per posology of treatment (19):
○ Proportion of patients who complete a 28-day cycle (21 days daily dose followed by 7 days off treatment).○ Mean (SD) of completed 28 day cycles.○ Proportion of patients co-administered letrozole at palbociclib initiation.○ Proportion of patients co-administered fulvestrant at palbociclib initiation.	
• Palbociclib: date on initiation, initial dose, date of dose reduction, subsequent dose, dates of cycle initiation and completion, date of discontinuation (indicate whether last cycle is interrupted or completed), reasons for palbociclib dose reduction / increase / discontinuation.• Date of start and end of concomitant medication treatment: letrozole, fulvestrant, osteo-strengthening drugs (denosumab, zometa), other drugs.• First 3 lines of medication after palbociclib discontinuation: name, dose and length of treatment.

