 - Number of lines of prior chemotherapy for metastatic disease
 - Proportion of patients for whom an LHRH was used
 - Proportion of patients treated with endocrine therapy in the neoadjuvant or adjuvant setting
 - Endocrine therapy name
 - Proportion of patients treated with endocrine therapy in the advanced/disease modifying/metastatic setting
 - Endocrine therapy name
 - Number of lines of prior endocrine therapy for metastatic disease
- Proportion of patients treated with radiotherapy in the advanced/disease modifying/metastatic setting
- Concomitant medications (defined as medications prescribed whilst on palbociclib)
- Concomitant medications prescribed alongside goserelin

PFIZER CONFIDENTIAL

- Number of prior treatments in the metastatic setting, all prior therapies as well as chemotherapy/endocrine therapy combined and separately

[figure not shown]
Secondary Objective 1: To describe treatment pattern (as per licence/IPP requirement); including the proportion of patients with dose modification and who switch treatment 1, 2 and 3 years after palbociclib initiation, and median time to dose modification and treatment discontinuation ('drug survival'). For patients who progress, to describe the 1st /2nd /3rd line of treatment after progression.

- Summary measures of palbociclib treatment patterns including:
 - Starting Dose.
 - Endocrine partner prescribed alongside palbociclib
 - Proportion of patients with dose reductions at 1, 2 and 3 years after initiation.
 - Proportion of patients with palbociclib treatment discontinuation at 1, 2 and 3 years after initiation.
 - Reasons for discontinuation of palbociclib
 - Proportion of patients with temporary discontinuations
 - Time to dose reduction in number of days (from start of treatment) – 1st line treatment group only
 - Time to palbociclib discontinuation ('drug survival') in number of days (from start of treatment) in those patients permanently discontinuing palbociclib
 - Reasons for discontinuation.
 - 1st, 2nd, and 3rd line of treatment after progression: number of patients prescribed each medication, dose, and length of treatment.
- Description of the number of patients which are being prescribed as per posology of treatment.
 - Number of completed 28-day cycles per patient.
 - Proportion of patients co-administered letrozole at palbociclib initiation.
 - Proportion of patients co-administered fulvestrant at palbociclib initiation.

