Proposed: Starting and mean dose of palbociclib and subsequent treatments after progression, length of treatments and time to dose reduction and discontinuation of palbociclib in days will be summarised as quantitative variables (see section 8.1.1). Times will be calculated in days through subtracting the time of first dose reduction/discontinuation from the date of palbociclib initiation. Treatment after progression and reasons for discontinuation, the proportion of patients completing a daily cycle, having dose reductions, treatment discontinuation and being co-administered letrozole and fulvestrant at palbociclib initiation will be summarised as categorical variables using frequencies and percentages (see section 8.1.2). Reasons for discontinuation of palbociclib will be presented as categorical data (see section 8.1.2) The proportions of patients with dose reductions and discontinuation will be calculated separately at 1 and 2 years after palbociclib initiation. Quantitative discrete variables (such as the number of completed cycles per patient) will be summarised using a combination of the approaches described in sections 8.1.1 and 8.1.2, if appropriate.

Actual: Starting dose of palbociclib was presented as a categoric variable as per section 8.1.2. Endocrine partner prescribed alongside palbociclib, proportion of patients with recorded dose reductions, proportion of patients who discontinued palbociclib and the associate reasons, proportion of patients with temporary interruptions to palbociclib treatment were presented as categoric variables as per section 8.1.2. Time to dose reduction was presented as a categoric variable as per section 8.1.2 (Categories: Patient did not have a dose reduction, dose reduction occurred within 3 months of palbociclib initiation, dose reduction occurred between 3 and 6 months after palbociclib initiation and dose reduction occurred over 6 months after palbociclib initiation). Number of patients

PFIZER CONFIDENTIAL

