prescribed treatment in the 1st, 2nd, and 3rd line after palbociclib discontinuation was presented as a categoric variable as per section 8.1.2. Dose, duration of subsequent treatments and number of completed 28-day cycles per patient were presented as quantitative variables as per section 8.1.1. Number of completed 28-day cycles (categories: 1-6 cycles, 7-12 cycles, 13-18 cycles, 19-24 cycles, 25-27 cycles and No completed cycles) and the proportion of patients co-administered letrozole or fulvestrant were presented as categoric variables as per section 8.1.2. All other endpoints were evaluated as proposed.

8.2.3 Secondary Objective 2: To describe overall survival and progression-free survival, response (CR, PR), stable disease. This includes estimating the proportion of patients achieving those endpoints at 1 and 2 following palbociclib initiation: median survival, time to response and duration of response. In patients who respond to treatment, to describe PR and CR using “swimmer plots”.

Proposed: For the estimation of the proportion of patients alive, and free from disease progression, the denominator will be all patients known to be alive at the selected time-points (e.g., 1 years, 2 years, and 3 years). For the estimation of the proportion of patients achieving PR, CR and with stable disease at the selected time-points (1 years and 2 years), the denominator will be all patients with at least one assessment of response (CR / PR / no response or stable disease / progressive disease) in the past year.

[figure not shown]
Actual: Proportion of patients free from disease progression, are alive, achieved PR, CR or stable disease were analysed separately at the 2-year timepoint only. Length of follow-up, and time to best response and first response were presented as quantitative variables as per section 8.1.1. Best response to palbociclib, overall and by de novo and relapse status was treated as a categoric variable and analysed according to section 8.1.2.

8.2.4 Secondary Objective 3: To describe the occurrence of neutropenia during the first-year post-initiation observation period.

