8.2.9 Summary of Analyses

Outcome	Analysis Set	Supports Protocol Objective Number	Subgroups	Statistical Method	Missing Data
Summary of age at initiation of palbociclib	Full Analysis set	Primary Objective	Overall and treatment Line	Calculated by subtracting Date of palbociclib initiation from Date of Birth. Summary statistics calculated (incl. Mean/Median/SD/IQR/Range)	Day of birth assumed to be the 15 th . If month is missing, birthday assumed to be 1 st July. Otherwise excluded.
Distributions of categorical, binary, and ordinal demographical and clinical characteristics	Full Analysis set	Primary Objective	Overall and treatment Line	Frequency tables and percentages	Excluded
Summary measures of MBC statistics	Full Analysis set	Primary Objective	Overall and Treatment Line	Frequency tables and percentages Summary statistics for Ki67 proliferation index (incl. Mean/Median/SD/IQR/Range)	Excluded
Duration of MBC at palbociclib initiation	Full Analysis set	Primary Objective	Overall and Treatment Line	Calculated by subtracting Date of palbociclib initiation from Date of MBC diagnosis. Summary statistics calculated (incl. Mean/Median/SD/IQR/Range)	Standard imputation for dates (section 7), otherwise exclude.
Treatment for MBC diagnosis prior to palbociclib initiation	Full Analysis set	Primary Objective	Overall and Treatment Line	Frequency tables and percentages	Excluded
Summaries of comorbidities and Charlson comorbidity index of patients at palbociclib initiation	Full Analysis set	Primary Objective	Overall and Treatment Line	Frequency tables and percentages for each comorbidity type Summary statistics calculated (incl. Mean/Median/SD/IQR/Range) for Charlson comorbidity index	Excluded
Palbociclib prescribed as on or off-label	Full Analysis set	Primary Objective	Overall and Treatment Line	Frequency tables and percentages	Excluded
Summary measures of palbociclib treatment patterns	Full Analysis set	Secondary Objective 1	Overall and Treatment Line	Frequency tables and percentages for proportions and categorical variables such as proportion of patients with dose reductions or discontinuation and reasons for discontinuation Summary statistics calculated (incl.	Excluded

PFIZER CONFIDENTIAL

				Mean/Median/SD/IQR/Range) for doses, time to dose reduction and discontinuation and length of treatment	

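### Protocol 9.3 limits dose intensity to patients who complete a treatment with no stated course length, and the SAP defines no summary combining dose, cycle delay and time on drug

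*Protocol*

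**What the plan says.** Among the treatment-pattern endpoints, Protocol 9.3 lists the mean (SD) of "dose intensity over the course of treatment in patients who complete treatment of palbociclib". It defines neither dose intensity nor completion. For the end of treatment it collects "dates of cycle initiation and completion, date of discontinuation (indicate whether last cycle is interrupted or completed"), together with reasons for discontinuation. The cycle it describes is "21 days daily dose followed by 7 days off treatment". No planned number of cycles or course length appears in either document.

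The SAP does not use the term dose intensity. Four places bear on the point:

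- SAP 8.2.2, Proposed text: quantitative summaries of "Starting and mean dose of palbociclib and subsequent treatments after progression, length of treatments and time to dose reduction and discontinuation". There is no formula, time base or rule for days off drug.
- SAP 8.2.9, row on palbociclib treatment patterns: summary statistics "for doses, time to dose reduction and discontinuation and length of treatment".
- SAP 6, Secondary Objective 1: starting dose, dose reductions, "Proportion of patients with temporary discontinuations", discontinuation and completed 28-day cycles. Neither dose intensity nor mean palbociclib dose is listed, although the section says it is meant to reflect what was analysed.
- SAP 8.2.2, Actual text: starting dose, reductions and interruptions are given as categories, then "All other endpoints were evaluated as proposed".

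**The concern.** A restriction to completers suits a regimen with a fixed course. Here treatment ends only when the patient stops, and the protocol analyses that as time to discontinuation. A rule that waits for completion either selects nobody who can be identified or selects patients because they stopped. The second reading removes those who stayed on drug longest. The direction of the resulting bias cannot be settled from the documents: patients who stopped for toxicity may have had more reductions and delays, while those who progressed early had little time to accumulate any.

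The SAP does not repair this. A reader of the final report could not tell from it whether any average dose was calculated, in whom, or over what time. Both documents name dose management as a focus of the study, and Protocol 7 describes interruption as well as reduction as reversing neutropenia. A summary of dose received over time is therefore something readers will look for.

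**Working it through.** The documents state no dose-intensity figure, so there is none to reproduce. The check has three parts.

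**1. Who falls outside the protocol's denominator, if completing means having stopped**

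Inputs:
- Horizons: 24 months (SAP 5.1 and 8.1) and 36 months (Protocol 9.3).
- Median time on drug: not given. I assume 15 to 24.8 months. The upper value is the median PFS that Protocol 7 quotes for the palbociclib arm of PALOMA-2, used as a proxy. The lower value is an assumption with no source in the documents.
- Shape: exponential, also an assumption.

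Share still on drug at time t = 0.5^(t / median):

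| Median (months) | 24 months | 36 months |
|---|---|---|
| 15 | 0.5^(24/15) = 33% | 0.5^(36/15) = 19% |
| 24.8 | 0.5^(24/24.8) = 51% | 0.5^(36/24.8) = 37% |

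With the SAP's approximate 200 patients, the 24-month column is about 66 to 102 people. A longer median excludes more: at 30 months, 0.5^(24/30) = 57% at 2 years.

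The SAP's own cycle bands suggest the excluded group is not empty. Its top band, 25-27 completed cycles, corresponds to 25 × 28 = 700 to 27 × 28 = 756 days, which is essentially the whole 2-year window.

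**2. What an average prescribed dose would miss, if that is what mean dose means**

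Input: the 21-on, 7-off cycle in Protocol 9.3. With an unchanged prescribed dose,

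relative intensity = ((21 − days missed) / (28 + days delayed)) / (21/28)

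- Every cycle lasting 35 days, no days missed: (21/35)/(21/28) = 0.60/0.75 = 80%.
- 7 days missed, no delay: (14/28)/(21/28) = 67%.

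The average prescribed dose is 100% in both cases. This tests one possible meaning of an undefined term, not a rule in the SAP.

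**3. Whether the other reported summaries fill the gap**

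Over 730 days on drug, 28-day cycles give 730/28 = 26 completed cycles and 35-day cycles give 730/35 = 20 (if a lengthened cycle counts as completed). These fall in different SAP bands, so delay leaves some trace. But 20 on-schedule cycles take 20 × 28 = 560 days, so a patient who kept to schedule and stopped at about 18 months has the same count as one delayed in every cycle for two years. Cycle count mixes duration with delay. The yes/no interruption item gives no days lost, and the dose-reduction items carry no time base.

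**The case against.** Several points on the other side are sound.

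- A reader might infer that the SAP replaces dose intensity with a mean dose that ignores interruptions. The documents do not support that. Mean dose is undefined, appears only as Proposed, and is missing from the SAP 6 list just as dose intensity is. SAP 8.2 also says that some proposed analyses were not conducted and were kept as a record. What can be shown is an omission and an internal inconsistency.
- A reader might conclude that delivered dose is not measured. That goes too far. Doses, dose-change dates and cycle dates are collected, and reductions, interruptions and completed cycles are reported. What is missing is one summary that combines them.
- Protocol 9.7 lets the SAP modify the plan and requires an amendment only for major changes to primary endpoints. Dropping a secondary descriptive item is allowed. But SAP 8.2 says it keeps unconducted proposals on record, and dose intensity is not among them.
- Completing could simply mean a finished exposure period, over which intensity is fully observed. That is a sensible motive, but it still selects on stopping. Intensity up to the data cut is also fully observed for patients still on treatment.
- Neither document plans to relate PFS or neutropenia to exposure, and the study controls for no confounding. The loss is descriptive; no planned inference is invalidated.

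**Conclusion.** The concern holds in this form. The protocol's denominator for dose intensity is a faulty rule and more than a missing detail: under one reading it cannot be identified, and under the other it excludes the longest-treated patients. The SAP contains no dose-intensity endpoint and contradicts itself on whether a mean dose was analysed.

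The size rests on assumptions. With exponential time on drug and a median of 15 to 24.8 months, 33% to 51% of patients would be excluded at 2 years and 19% to 37% at 3 years. The 2-year figures apply the protocol's rule at the SAP's cut; the 3-year figures match the protocol's own horizon. The contrast of 80% with 100% holds only if mean dose is the average prescribed dose. The absence of a planned end to treatment is inferred from the lack of any stated course length.

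This is a secondary descriptive endpoint. The primary objective is unaffected.

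**What to change.** 1. In Protocol 9.3, delete the restriction to patients who complete treatment.
2. In SAP 6, 8.2.2 and 8.2.9, define dose intensity for all patients with at least one dose: cumulative palbociclib dose, derived from recorded doses and cycle dates, divided by time from first dose to the earliest of permanent discontinuation, death, loss to follow-up or data cut. Express it per 28 days and relative to the schedule stated in Protocol 9.3. State the reference dose for the relative figure, since scaling to a patient's own starting dose would not show a reduced start.
3. Report it overall and by treatment line, with patients still on treatment included.
4. Reconcile the SAP 6 list, the Proposed and Actual text of 8.2.2 and the 8.2.9 row. Either define mean dose and list it, or record that it was not analysed.

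Cost: because the SAP describes analyses already done, this means some re-derivation as well as new wording. The main inputs are already listed for collection in Protocol 9.3. Days missed within a cycle are not explicitly collected, so the result is approximate and should be labelled so.

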9.4. Data sources

Data for this study will be collected through retrospective and prospective patient chart review from 8-9 cancer services of NHS Trusts in the UK. A feasibility pilot for data collection will be carried out on 10 of the initial patients' data collected. These patients will be selected from one or two centres (dependent on the speed of data capture) to enable the data to be reviewed at the earliest opportunity. The purpose of this pilot will be to check the availability and quality of data that will be collected in the study, and to confirm the length of time required to collect the data.

Data on patient demographic and clinical characteristics, treatment patterns, outcomes, healthcare resource use and AEs will be collected in deidentified-coded form, from paper based and/or electronic hospital medical records (as applicable at each site) by members of the patients' direct care team or pH Associates.

9.5. Study size

This is a descriptive study and there is no *a priori* hypothesis specified. Therefore the sample size has been chosen pragmatically, based on the available patients from the IPP.

Across the entire UK, 846 women received palbociclib as part of the IPP. In the sites selected for this study, approximately 250 patients (exact number will be updated after site confirmation and patient consent) received palbociclib as part of the IPP. All eligible patients within the selected sites will be recruited into the study.

9.6. Data management

Data management and handling of data will be conducted according to the study specific data management plan and in accordance with ENCePP/ISPE/ guidance and the General Data Protection Regulation and applicable national data protection legislation and regulations. Data for the study will be collected via an electronic data capture system using a standardised eCRF designed specifically for the study in accordance with this protocol. All data will be collected from hospital medical records by members of the NHS direct care team or an external researcher from pH Associates.

Before the start of data collection, NHS staff collecting data from patients' hospital medical records will be trained in data entry into the eCRFs by study management staff from pH Associates and consistency checks will be built into the eCRF to ensure data quality.

Patients will be identified in all study records by a unique study code to link multiple study records for each participant and preserve patient confidentiality.

Data management for eCRFs will be carried out using MACRO™, a data management system which has a secure web-based data entry interface and is fully validated and compliant with the International Council for Harmonization E6 Good Clinical Practice guidelines, FDA Information Governance standard 21 Code of Federal Regulations Part 11 and the EU Clinical Trials Regulation, and the UK Medicines and Healthcare products

Regulatory Agency requirements. The MACRO™ system has restricted access permissions for data entry and data management, and records an audit trail of all changes to data and activity in the system. Access to the study in MACRO™ will be restricted (by password protection) to only those members of staff directly involved with the study and assigned access permissions will control the level of access to that required for the role of each individual working on the study. If corrections are needed to an eCRF, queries will be raised in the electronic data capture system by the study data manager and these will be resolved by the responsible investigator (or designee) by reference to the source records or agreed assumptions.

After obtaining the appropriate local approvals for data release, the deidentified data for this study will be collated and transferred securely to pH Associates, who will be the Data Processor for data management, analysis and reporting on behalf of Pfizer, the Data Controller. Pfizer will not have access to individual patient level data. After the initial retrospective data collection, data will be collected prospectively up to a maximum of 3 years from enrollment in the IPP by members of the direct care team by updating the eCRF with any subsequent therapeutic and progression data available in the medical records until the end of the 3 year follow-up period.

9.6.1. Case Report Forms (CRFs)

As used in this protocol, the term eCRF should be understood to refer to an electronic data record.

An eCRF is required and should be completed for each included patient. The completed original eCRFs are the sole property of Pfizer and should not be made available in any form to third parties, except for authorised representatives of Pfizer or appropriate regulatory authorities, without written permission from Pfizer. The investigator shall ensure that the eCRFs are securely stored at the study site in encrypted electronic form and will be password protected or secured in a locked room to prevent access by unauthorised third parties.

The investigator has ultimate responsibility for the collection and reporting of all clinical, safety, and laboratory data entered on the eCRFs and any other data collection forms (source documents) and ensuring that they are accurate, authentic/original, attributable, complete, consistent, legible, timely (contemporaneous), enduring, and available when required. The eCRFs must be signed by the investigator or by an authorised staff member to attest that the data contained on the eCRFs are true. Any corrections to entries made in the eCRFs or source documents must be dated, initialed, and explained (if necessary) and should not obscure the original entry.

In most cases the source documents are the hospital or the physician's chart. In these cases, data collected on the eCRFs must match those charts.

In some cases, the eCRF may also serve as the source document. In these cases, a document should be available at the investigator site and at Pfizer that clearly identifies those data that will be recorded on the eCRF, and for which the eCRF will stand as the source document.

